12.2 Adverse Events

All reported AEs will be coded using the MedDRA with the most current version for the purposes of summarization. NCI CTCAE Version 5.0 will be used for grading AEs. AEs will be collected and recorded for each patient from the day of signing the ICF until 30 days after last trial intervention administration or until participant started alternative anticancer

therapy, whichever is sooner. Prior to receiving trial intervention, only AEs considered related to trial procedures, and all serious adverse events (SAEs) will be summarize by study phase and treatment arms.

A treatment-emergent adverse event (TEAE) will be defined as any event that was not present prior to the initiation of trial intervention(s) or any event that worsens in either intensity or frequency following exposure to trial intervention(s) through 30 days after cessation of trial treatment or until the participant starts alternate anti-cancer therapy, whichever is sooner, with exception of treatment related SAEs which were reported until the end of survival follow-up and will be included as TEAE regardless of time of onset.

All TEAEs reports will summarize by dose levels and dose schedules unless otherwise specified.

Overall TEAE summaries will be presented for the Safety Population. The summaries will include the following categories:

- All TEAEs
- TEAE by CTCAE grade
- TEAEs with CTCAE Grade ≥ 3
- TEAE leading to study treatment discontinuation
- TEAE leading to death
- TEAE related to study treatment
 - TEAEs related to study treatment are defined as 'definitely related', 'probably related', or 'possibly related', to study drug as assessed by the Investigator.
- TEAE related to study treatment with CTCAE Grade ≥ 3
- TEAE related to study treatment leading to treatment discontinuation
- TEAE related to study treatment leading to study treatment interruption
- TEAE related to study treatment leading to study treatment reduction
- TEAE related to study treatment leading to death
- Serious TEAE
- Serious TEAE leading to treatment discontinuation
- Serious TEAE leading to death
- Serious TEAE related to study treatment
- Serious TEAE related to study treatment leading to study treatment discontinuation
- Serious TEAE related to study treatment leading to death

Any missing onset date, causality, or severity must be queried for resolution. Unresolved missing causality will be handled according to the following rules:

An unresolved missing causality will be considered "Related".

The following summaries by SOC and PT will be sorted by decreasing frequency of subjects within each SOC and then similarly by decreasing frequency of subjects within each PT. In the case of equal frequency of number of subjects in SOCs or PTs, summaries will be sorted descending order.

- TEAEs by SOC and PT
- TEAEs with Grade \geq 3 by PT
- TEAEs leading to study treatment discontinuation by SOC and PT
- TEAEs leading to death by SOC and PT

- TEAEs by maximum NCI-CTCAE grade by SOC and PT
- Treatment-related TEAEs by SOC and PT
- Treatment-related TEAEs with Grade \geq 3 by PT
- Treatment-related TEAEs leading to treatment discontinuation by SOC and PT
- Treatment-related TEAEs leading to death by SOC and PT
- Serious TEAEs by SOC and PT
- Most frequent TEAE (>= 10% in total) by PT
- Most frequent treatment-related TEAE (>= 5% in total) by PT

If a SOC or PT was reported more than once for a subject, the subject would only be counted once in the incidence for that SOC or PT.

All AEs will be listed by patient, along with information regarding onset, duration, relationship and severity to study drug, action taken with study drug, treatment of event, and outcome.

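### The TEAE exception for treatment-related SAEs in SAP 12.2 has no first-dose lower limit, so a pre-dose SAE can be flagged as a related serious TEAE if programmed literally (minor)

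*SAP*

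**What the plan says.** Everything that bears on the flag stands in SAP 12.2 (Adverse Events).

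- **Collection.** "AEs will be collected and recorded for each patient from the day of signing the ICF", so events before the first dose are in the database.
- **Pre-dose reporting.** "Prior to receiving trial intervention, only AEs considered related to trial procedures, and all serious adverse events (SAEs) will be summarize by study phase". All pre-dose SAEs are therefore kept, whatever their cause.
- **TEAE, start of window.** A TEAE is "any event that was not present prior to the initiation of trial intervention(s) or any event that worsens in either intensity or frequency" after exposure.
- **TEAE, end of window.** The window runs "through 30 days after cessation of trial treatment or until the participant starts alternate anti-cancer therapy, whichever is sooner".
- **Exception.** The same sentence then excepts "treatment related SAEs which were reported until the end of survival follow-up and will be included as TEAE regardless of time of onset".
- **Missing causality.** "Any missing onset date, causality, or severity must be queried for resolution". If the query fails, "An unresolved missing causality will be considered" Related. No onset limit is attached. SAP 7.10 confirms that this imputation concerns relationship to study drug.

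TEAE incidence and severity is a primary endpoint (Protocol synopsis; SAP 5.2). SAP 12.2 reports TEAEs by dose level and schedule, with rows for serious TEAEs related to study treatment.

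**The concern.** The exception applies to the TEAE definition as a whole. That definition has two limits: first dose at the start, and 30 days or new therapy at the end. Lifting the end limit for related SAEs makes sense, because a drug-related SAE can appear late. Lifting the start limit does not, because an event that preceded the drug cannot have emerged on it. The exception as worded removes both.

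The causality rule makes this more than a theoretical gap, since it can supply the related status that brings a pre-dose SAE under the exception. Pre-dose SAEs are plausible here: SAP Appendix 14.1.1, Table 1, requires a screening biopsy when archival tissue is inadequate.

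At stake is the classification behind the primary endpoint. It matters most in the related serious rows, where counts are small and tables are split by dose level. Two programmers could reasonably flag the same record differently.

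**Working it through.** The plan states no figure for this point, so there is nothing to reproduce. The check applies the SAP 12.2 rules to each type of event, first as worded and then with a first-dose limit added to the exception.

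**Rules as coded**

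- Related = recorded as definitely, probably or possibly related, or missing and unresolved after query.
- In window = onset from first dose to 30 days after last dose, with no new therapy started.
- TEAE as worded = in window, or (serious and related).
- TEAE with limit = in window, or (serious and related and onset on or after first dose).

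**Is the event a related serious TEAE?**

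| Onset | Serious | Causality | As worded | With limit |
|---|---|---|---|---|
| Before first dose | Yes | Missing, unresolved | Yes | No |
| Before first dose | Yes | Possibly related | Yes | No |
| Before first dose | Yes | Unrelated | No | No |
| Before first dose | No | Any | No | No |
| In window | Yes | Missing or possibly related | Yes | Yes |
| In window | Yes | Unrelated | No (TEAE, not related) | No (TEAE, not related) |
| After window | Yes | Missing or possibly related | Yes | Yes |
| After window | Yes | Unrelated | No | No |

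Non-serious events in or after the window are classified the same way under both versions. The limit changes only the first two rows.

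**Worked case.** Consent on Day -20; an SAE of biopsy bleeding on Day -12; the participant is then dosed; drug causality is blank and the query is not resolved. The causality rule makes the event Related. The exception then makes it a TEAE. It enters the related serious row and also qualifies for the pre-dose SAE summary. With the first-dose limit it appears only in the pre-dose summary.

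**Size of one case**, as 100 / n percentage points:

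- n = 3 (minimum cohort at and after Dose Level S, SAP 4.1): 100/3 = 33.3
- n = 20 (one expansion cohort, SAP 4.3): 100/20 = 5.0
- n = 40 (escalation, or both expansion cohorts, SAP 4.3): 100/40 = 2.5
- n = 80 (all exposed, SAP 4.3): 100/80 = 1.25

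One case can also move a preferred term from 3/80 = 3.75% to 4/80 = 5.0%, which reaches the 5% cut-off for the table of most frequent treatment-related TEAEs in SAP 12.2.

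**The case against.** The strongest reply is that the context already settles the meaning. The exception follows directly on the end-of-window clause and speaks of survival follow-up. The base definition in the same sentence excludes events present before the first intervention. SAP 7.4 imputes partial AE dates against the first dose date to decide treatment emergence, which presupposes a first-dose limit. Pre-dose SAEs have a summary of their own. Missing causality must be queried before anything is imputed. And *Related* by imputation is not one of the three investigator categories that SAP 12.2 uses to define a related TEAE.

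Most of this stands. It shows what was intended and makes misclassification unlikely, so a reader should not infer that it is certain. It does not close the gap. An exception overrides the definition it is attached to, so the base definition cannot by itself restore the lower limit. Nothing makes the pre-dose summary and the TEAE tables mutually exclusive. The imputation rule exists for queries that fail. The mismatch between imputed *Related* and the three investigator categories is one more ambiguity, not a safeguard.

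The reply also notes that all AEs are listed with onset and relationship, so a misclassified case would be visible, and that the analysis is descriptive (SAP 7). Both are true, and both bear on severity.

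**Conclusion.** The point holds as a minor wording defect. The exception lacks a first-dose lower limit, and a literal programme can count a pre-dose SAE as a treatment-related serious TEAE. This requires that the participant is later dosed, that the event is recorded as related or its causality stays missing after query, and that the programmer follows the words rather than the evident intent. One case is 1.25 points in 80 participants or 33 points in a cohort of 3.

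Four stronger conclusions might be drawn, and the documents do not support them:

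- **An expected number of cases.** The documents give neither a rate of pre-dose SAEs nor a rate of unresolved causality. Only the size of a single case can be stated.
- **False entries among fatal events.** The Safety Population requires at least one dose (SAP 6.2), so a death before dosing is not in these tables. A pre-dose event that worsens to death after dosing is already a TEAE under the base definition.
- **An effect on DLT counts.** SAP 12.1 counts DLTs only from the first dose to the end of Cycle 1, so a pre-dose SAE cannot become a DLT through this rule.
- **A faulty missing-causality rule.** Once the exception has a first-dose limit, imputing *Related* to a pre-dose event no longer makes it a TEAE.

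**What to change.** Reword the exception in SAP 12.2 along these lines: *treatment-related SAEs with onset on or after the first dose of RP-1664 are included as TEAEs even if onset is more than 30 days after the last dose or after the start of alternate anticancer therapy.* Leave the missing-causality rule unchanged.

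The cost is one clause in the SAP and one condition in the TEAE flag. The table of cases above shows that no in-window or late event changes classification. A pre-dose event that worsens after dosing remains a TEAE under the base definition. The change should be made before database lock.

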4.1 Study Design

The trial will follow a Bayesian Optimal Interval (BOIN) design to guide escalation and de-escalation decision, establish a maximum tolerated dose (MTD), and identify a dose and schedule of RP-1664 that is tolerable.

All participants will undergo a PK evaluation period starting at Cycle 0 Day 1. Participants will be assigned to receive either a single dose of RP-1664 at the highest Safety Review Committee (SRC) approved dose level with PK collection over the subsequent 48 hours to characterize the half life (t1/2) of RP-1664 in the fasted state or enrolled into a cohort to investigate the effect of food on RP-1664 PK.

The starting dose (Dose Level 1) is 10 mg once daily (QD). RP-1664 will initially be given QD on a 2 weeks on 1 week off schedule to allow 1 week for bone marrow recovery.

The first escalation (Dose Level 2) will be up to 30 mg to limit the number of participants receiving a potentially subtherapeutic dose. After Dose Level 2, escalation will proceed with up to 100% increases in RP-1664 after evaluation of tolerability by the SRC until Dose Level S. Dose Level S is defined as the dose level at which any of the following safety signals occur during Cycle 0 or Cycle 1:

- Any \geq Grade 3 hematological toxicity
- >50% decrease in platelets or neutrophils from Cycle 0 Day 1
- >2 g/dL decrease in hemoglobin from Cycle 0 Day 1
- Any ≥ Grade 2 drug-related non-hematological toxicity lasting >5 days or requiring clinical intervention, except Grade 2 fatigue, nausea, vomiting, diarrhea, or constipation
- Any adverse event (AE) of any grade limiting tolerability as assessed by the SRC

At Dose Level S, the cohorts will be expanded to a minimum of 3 participants to further evaluate safety, PK, and pharmacological activity. Evidence of pharmacologic activity can include Grade ≥ 2 drug-related toxicity at any cycle, PK

data demonstrating exposure levels predicted to be efficacious based on nonclinical studies, or other evidence of treatment-related activity as agreed on by the SRC. Dose decisions will be based on assessments in 2 or more dose-limiting toxicity (DLT) evaluable participants completing the DLT evaluation period. Any escalation of RP-1664 after Dose Level S will be in increments up to 75% as agreed upon by the SRC and will enroll cohort sizes of $N \ge 3$.

RP-1664 Escalation Dose Level	Escalation Plan
	Daily (mg) or % of previous dose
	increment
1	10 mg
2	Up to 30 mg
3 to S	Up to 100% increases until Dose Level S

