12.1 Dose Limiting Toxicities

The number of DLTs will be summarized by treatment arms for the DLT Evaluable Population. A toxicity will be considered a DLT if it occurs from the first dose to the end of Cycle 1 (including the PK evaluation period), meets the pre-defined criteria for DLTs, is deemed at least possibly related to trial treatment, and is not clearly and incontrovertibly due to disease progression or extraneous cause. Toxicity will be assessed using CTCAE v 5.0, unless other specified. Details of DLTs will be listed.

DLTs will be defined as any of the following:

Any death not clearly due to the underlying disease or extraneous causes

Hematologic TEAES:

- Grade 4 neutropenia
- Febrile neutropenia (defined as absolute neutrophil count (ANC) <1000 cells/ μ L with a single temperature of 38.3°C [100.4°F] for > 1 hour).
- Grade 4 thrombocytopenia or Grade 3 thrombocytopenia associated with Grade \geq 2 bleeding.
- Grade 4 anemia or Grade 3 anemia requiring red blood cell (RBC) transfusion given to participants with documented anemia-related symptoms.

Non-Hematologic TEAEs:

- Any Grade \geq 3 TEAE except the below
 - 1. Grade ≥ 3 non-hematologic laboratory abnormalities that are asymptomatic and respond to medical intervention or resolve to grade 1 in \leq 72 hours.
 - 2. Grade 3 fatigue with duration < 7 days
 - 3. Grade \geq 3 nausea/vomiting/diarrhea that lasts \leq 72 hours and resolves with or without optimal supportive care.
 - 4. Grade \geq 3 amylase or lipase elevation not associated with symptoms or clinical manifestations of pancreatitis.
 - 5. The use of red blood cell transfusion for anemia Grade <3 or the use of G-CSF for Grade <4 neutropenia
- Symptomatic Grade ≥ 3 QTc prolongation (QTcF ≥ 501 msec on at least two separate electrocardiogram (ECGs)), or asymptomatic Grade ≥ 3 QTc prolongation that has been confirmed by repeat testing and reevaluation by a qualified person and persists after correction of reversible causes such as electrolyte abnormalities or hypoxia.
- Drug-induced liver injury meeting Hy's Law criteria defined as:
 - 1. ALT or AST ≥3-fold above the Upper Limit of Normal (ULN) or 5.0 x ULN in the case of liver metastases at baseline and
 - 2. Serum total bilirubin \geq 2-folde above ULN (without findings of cholestasis) and
 - 3. Alkaline phosphatase $\leq 2 \times ULN$ and
 - 4. No other overt reason for liver injury

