12.3 Clinical Laboratory Tests

Selected hematology and serum chemistry parameters including Alanine Aminotransferase (ALT), Aspartate Aminotransferase (AST), Creatinine, Total Bilirubin, Hemoglobin, Neutrophiles and Platelets Count will be summarized for Safety population. All other laboratory results, including pregnancy test results, will be listed only.

For all quantitative parameters, the actual value and the change from baseline by scheduled time of evaluation will be summarized by dose levels and dose schedule for each study visit using descriptive statistics. Both scheduled and unscheduled visits will be considered for baseline derivation.

Laboratory parameters are also graded according to CTCAE v5.0 for the selected parameters listed above. A shift table, presenting the 2-way frequency tabulation for baseline and the worst post-treatment value according to the NCI-CTCAE grade, will be provided. Laboratory parameters with CTCAE grading in both high and low directions will be summarized separately. Both scheduled and unscheduled post-treatment visits will be considered in tabulation of the worst post-treatment value. Additionally, the number and percentage of participants with the following potentially clinically significant abnormal liver function test will be presented:

- ALT >3xULN, \geq 5xULN, \geq 10xULN, and \geq 20xULN
- AST >3xULN, \geq 5xULN, \geq 10xULN, and \geq 20xULN
- Total bilirubin >2xULN

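### SAP 12.2 defines no grouped terms: if one cytopenia is coded to more than one preferred term, the TEAE tables only bound its combined incidence (minor)

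*SAP*

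**What the plan says.** SAP 12.2 states that "All reported AEs will be coded using the MedDRA with the most current version for the purposes of summarization". It then lists twelve term-level TEAE tables. Eight are by SOC and PT; an example is "Treatment-related TEAEs leading to treatment discontinuation by SOC and PT". Four are by PT alone: Grade 3 or higher, treatment-related Grade 3 or higher, and two abbreviated tables, "Most frequent TEAE (>= 10% in total) by PT" and "Most frequent treatment-related TEAE (>= 5% in total) by PT". When a term recurs within a participant, "the subject would only be counted once in the incidence for that SOC or PT". That is the only counting rule. The text available contains no grouped term, combined-PT rule or standard query.

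Outside the TEAE tables, SAP 12.3 plans this for hemoglobin, neutrophils and platelets, among other parameters: "A shift table, presenting the 2-way frequency tabulation for baseline and the worst post-treatment value according to the NCI-CTCAE grade". SAP 12.2 also plans a listing of all AEs that includes relationship, severity and action taken.

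**The concern.** Incidence and severity of TEAEs is a primary endpoint. The protocol synopsis names neutropenia as an expected human toxicity and justifies the week off treatment by marrow recovery. All three cytopenias are dose-limiting toxicity (DLT) criteria in SAP 12.1.

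The documents themselves describe these toxicities in two ways. SAP 12.1 uses condition names, as in "Grade 4 anemia or Grade 3 anemia requiring red blood cell (RBC) transfusion". SAP 4.1 defines Dose Level S partly by laboratory change, as in more than a "2 g/dL decrease in hemoglobin from Cycle 0 Day 1". The trial is multi-site and multi-regional, with safety laboratory tests run locally. If investigators report in both styles and the coding keeps them apart, one cytopenia will sit in two PT rows. Participants are de-duplicated within each row but not across rows. A SOC row does not help, because it pools every term in that class.

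A reader asking how many participants had treatment-related, serious or Grade 3 or higher low neutrophils, or stopped treatment for it, would then get a range and not a count.

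**Working it through.** **Inputs.** About 80 participants exposed (SAP 4.3). Cut-offs of 10% and 5% in total, applied per PT (SAP 12.2). Assumptions not in the documents: one cytopenia is split over two PTs, and N could lie between 70 and 90 because 80 is approximate. The plan gives no figure of its own to reproduce on this point.

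**1. Bound on combined incidence.** If two PT rows hold a and b participants, the number with either term lies between max(a, b), when the smaller row is wholly contained in the larger, and a + b, when no participant has both.

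- Rows of 16 and 8: 16 to 24 participants, that is 16/80 = 20% to 24/80 = 30%.
- Rows of 12 and 12: 12 to 24 participants, that is 12/80 = 15% to 24/80 = 30%.

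The same bound applies in each term-level table. If only one component PT has participants in a given table, a = a + b and the count is exact.

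**2. Understatement by the largest row.** This is 1 − max(a, b)/(number with either term).

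- Full overlap: the denominator equals max(a, b), so 0%.
- No overlap, 24 and 0 (no split): 1 − 24/24 = 0%.
- No overlap, 17 and 7: 1 − 17/24 = 29%.
- No overlap, 12 and 12: 1 − 12/24 = 50%.

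**3. Absence from the two abbreviated tables, N = 80.**

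| Table | Fewest participants to be listed | Most in an unlisted row | Two unlisted rows combined |
|---|---|---|---|
| TEAE, 10% | 8 (8/80 = 10.0%) | 7 (8.75%) | 7 to 14 (8.75% to 17.5%) |
| Related TEAE, 5% | 4 (4/80 = 5.0%) | 3 (3.75%) | 3 to 6 (3.75% to 7.5%) |

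**4. Sensitivity of the maxima to N.**

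| N | 10% table | 5% related table |
|---|---|---|
| 70 | 6 + 6 = 12/70 = 17.1% | 3 + 3 = 6/70 = 8.6% |
| 80 | 7 + 7 = 14/80 = 17.5% | 3 + 3 = 6/80 = 7.5% |
| 81 | 8 + 8 = 16/81 = 19.8% | 4 + 4 = 8/81 = 9.9% |
| 90 | 8 + 8 = 16/90 = 17.8% | 4 + 4 = 8/90 = 8.9% |

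Over all N from 70 to 90 the maxima run from 17.1% to 19.8% for the 10% table and from 7.5% to 9.9% for the 5% table.

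**5. What other outputs recover.** The SAP 12.3 shift table gives participant-level worst laboratory grade for neutrophils, platelets and hemoglobin, whatever the PT. It carries no relatedness, seriousness or discontinuation. The overall TEAE summary is independent of PT but counts any TEAE, not a named toxicity. The AE listing allows a manual recount by relationship and action taken; seriousness is not among the fields that SAP 12.2 names for it.

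**The case against.** The strongest reply is that the trigger is assumed. Nothing in the documents shows that a cytopenia will be coded to more than one PT. Only the protocol synopsis is available, so a coding convention may exist elsewhere, and zero effect lies within the stated range. This stands, and it is why the point is conditional.

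The second reply is that the clinical question is largely answered already. The shift table gives worst-grade incidence for exactly these three parameters, and DLTs are assessed against clinical criteria, not PTs. This also stands. What remains open is relatedness, seriousness and discontinuation for a split term, and a combined count of reported TEAEs by grade. A recount from the listing is possible, but the component terms would be chosen after the data are known in an open-label trial. Pre-specification removes that discretion.

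The third reply is that the analyses are descriptive and no statement in the SAP is wrong. That is correct. The point is a better tabulation of a primary endpoint, not the correction of an error.

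A reader might infer that the combined related, serious or discontinuation incidence would be unobtainable. The tables do not support that: the figure is bounded, and it is exact when only one component PT occurs. Nor do 17.5% and 7.5% mean that events vanish from reporting. They concern two abbreviated tables, need rows just under the cut-off with no overlap, and leave every PT in the full SOC and PT tables.

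**Conclusion.** The point holds as a minor, conditional one. SAP 12.2 has no grouped terms. If a cytopenia is split over PTs, the TEAE tables fix its combined incidence only between the largest row and the sum of the rows. This applies equally to the related, serious, Grade 3 or higher and discontinuation tables. For a two-way split, the understatement by the largest row is anywhere from 0% to 50%. The documents give no basis for choosing a value in that range.

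A reader might go further and infer that safety decisions in the trial are at risk. They are not. DLTs rest on the SAP 12.1 criteria and Dose Level S on the SAP 4.1 safety signals, and neither uses PT counts. The effect is confined to how clearly the final tables report the anticipated toxicity.

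**What to change.** In SAP 12.2, pre-specify three grouped rows: low neutrophils, low platelets, and anemia/low hemoglobin.

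- Fix the component PTs of each group before database lock.
- Count each participant once per group at worst grade; in the treatment-related tables, use the worst grade among related events.
- Show each group beside its component PTs in the all-TEAE, maximum-grade, Grade 3 or higher, treatment-related, serious, discontinuation and most-frequent tables.
- Apply the 10% and 5% cut-offs to the groups as well as to single PTs.
- Keep febrile neutropenia as its own row, since it is a separate DLT criterion.

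The cost is a short term list, minor programming and slightly longer tables; no new data are needed. If coding turns out uniform, each grouped row equals its PT row and nothing is lost.
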